### Sampling Duration, Time Frame, and work plan:

Background /Pilot Study	Survey	Observation Period (1 st Data Set/Phase 1 )	Washo ut	Survey	Observation Period (2 nd Data Set/ Phase 2)	Wash out	Survey	Observation Period (3 rd Data Set/ Phase 3)
8 weeks	4 weeks	4 weeks	3 week	2 Week	4 weeks	3 week	2 week	4 weeks
04 Sep -30 Oct (2017)	31 Oct – 28 Nov (2017)	01 Dec - 30 Dec (2017)	1st Jan - 05 Feb (2018)		06 Feb – 08 Mar (2018)	26 Mar – 30 Apr (2018)		22 May – 20 Jun (2018)
		8 curtains from Male  12 curtains from Female Cubicle  50% coated curtain, 50% standard curtain			12 Curtains from Male Cubicles  12 Curtains from Female Cubicle  50% coated curtain, 50% standard curtain			16 Curtains from Male Cubicles  16 Curtains from Female Cubicle  50% coated curtain, 50% standard curtain
		No of samples: 480			No of samples: 576			No of samples: 768

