## **Detailed Description:**

[1] A multi-level antimicrobial coating was produced in the HKUST laboratory using the newly developed staged flow micromixing to prepare contact-killing and anti-adhesion coating made of US-FDA approved polymeric materials. The process was optimized to scale-up the production to 5 liters per hour. 300 liters of the multi-level antimicrobial coating was prepared for the study for a total of 24 weeks as three liters of the coating was needed for one patient privacy curtain.

[2] The study was conducted in the rehabilitation ward of the Kowloon Hospital including both male and female cubicles. It was carried out in three stages with each stage consisting of survey and a four weeks' observation period, separated by three weeks' washout period. In the rehabilitation ward of Kowloon Hospital, a set of male and female cubicle was recruited for the study after getting maximum number of bacterial contamination on patient privacy curtains in pilot study of 8 weeks. Each cubicle had 12 curtains besides admitted patients where all the samples are collected.

[3] Environmental sampling was carried out using sponge swab on the surfaces of the patient privacy curtains. The total bacteria count and quantitative isolation of MRSA was done using established protocols. The total bacteria count provides a quantitative measure of surface cleanliness, while the MRSA count was indicative of the risk of contact transmission from contaminated surfaces. 2-4 weeks survey provided control data on the cleanliness of patients privacy curtains in terms of total bacteria and MRSA counts.

During the study period, the Kowloon Hospital/Queen Elizabeth Hospital infection control team monitored MDROs regularly as part of their routine operation. The procedure and schedule was followed strictly the infection control protocol. All infection control measures implemented after isolation of MDROs were followed according to the hospital's usual practice as advised by the infection control team. In the study, the identification of the organisms in patients more than 48 hours after admission without prior isolation of the organisms in clinical or screening specimens was defined as nosocomial.

[4] The investigators demonstrated a cross-over intervention study. In the first stage of study, half of the patient privacy curtains were considered as treatment (antimicrobial coated) and the other

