half of the curtains as control in the same setting in a cubicle. As the study was double blind, so coding was done to identify the treatment as control curtains.

[5] Sample were taken from eight highly touched areas of 50x50 cm^2 on weekly bases for three consecutive weeks on 7th day of first installation. On each period/phase 480, 576 and 786 samples were collected accordingly using the developed sample protocol. In total, the investigators collected 1824 samples from 76 patient privacy curtains in which 912 (50%) were control curtain and 912 (50%) are antimicrobial coated curtains.

[6] Healthcare workers from the participating wards were assessed for their acceptance of the multilevel antimicrobial disinfectant coating by way of a questionnaire. Additional reformulation may be necessary to increase the acceptability of the coating technology to the healthcare workers.

[7] For the bacteria count, duplicate plates of TSA (total bacteria count) and Chromagar MRSA (selective agar for MRSA detection) were used for enumeration. CFU/m^2 is calculated after 48 hours' incubation at 37C. Data was analyzed using SPSS V.21 to assess the effectiveness of the coating in reducing the contamination level of the surface. The total bacteria count on the patient privacy curtains was compared between the control and treatment group using Mann-Whitney test and T-test. ANOVA analysis allowed the comparison of different periods of study of phase wise as well as week wise. The significance of the statistical test is defined to have a P value <0.05.

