## **Sampling Arrangements and methods:**

1. Sampling Cubicles (Location): one male cubicle (3rd cubicle) and one female cubicle were allocated for this study after pilot study results. These were located on 3rd floor or rehabilitation building (ward 3B).

2. Sampling time: Every visit, sampling was started at 8:30 am and finished till 12:00 pm.

3. Following the Rules: Sampling team had to follow the rules of Kowloon Hospital in rehab wards. The team had to sample curtains smoothly and quietly to minimize disturbance to working staff as well as patients in beds. The team was not allowed to encroach patient treatment or investigations/ file to keep the confidentiality.

4. Gowning for safety: All the members were gowned properly by wearing personal protective equipment (disposable gown, gloves, mask and head cover). For gowning, individual followed the step mentioned in safety training, as all sampling taking persons had gone through safety training by infection control team of Kowloon Hospital.

5. Sample taking notification and Consent: Team was notifying ward manager/ ward in-charge about sampling plan and take verbal permission to proceed.

6. Sampling Teams: In the female cubicle, two female team members took samples. One

member was take a sample of swabbing the area; other was helping to provide gloves, sponge, identification of appropriate area, calibrate the size and provide support by holding the frame of 50x50cm^2. The same sampling protocol was adopted in a male cubicle where male team members were taking the samples.

7. Safety precaution:

Following safety measures were accomplished before and during sampling:

- a. Before sampling, clean the hands having gloves with available disinfectant.
- b. Put plastic disposable gloves and take out sponge from its plastic packing.
- c. Again disinfect plastic gloves and let it dry for few second.
- d. Hold the sponge firmly from one side and keep sampling designed 50x50cm^2 area.
- e. Don't touch any other, other area holding the sponge, and prevent felling down on contaminated floor
- f. In case, sponge was touch with other surface or fell on floor, please discard that sponge and resample the same area with a new sponge

8. Sample preservation:

- a. After proper sampling, we put the sponge in zipped plastic bag containing 10 ml neutralizing solution quickly to reduce chance of contamination

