### **Data Analysis:**

The duplicate system in total bacteria count helped to monitor the validity of the data point. Logical elimination of plate count was determined while comparing the bacteria morphology of the first plate with the second plate. If the bacteria morphology was not consistent, the plate with more bacteria was eliminated, and the plate with a lower value was taken due to the chance of contamination on a non-selective agar plate.

The Colony Forming Unit (CFU) obtained on the duplicated plates was averaged, and the CFU per unit area was calculated. CFU per unit area was allowing the comparison of microbiological contamination of the sampled surface. With the dilution factor of the samples, the Total bacteria count (TBC) was determined. The microbiological contamination level of an item was represented by the CFU/unit area of the item.

CFU on Müller-Hinton Agar represents the total aerobic bacteria count. By dividing the CFU with the area sampled, CFU/m^2 was obtained. Data points that did not contain any CFU count were assumed to have 0.5 CFU. The assumption was made based on the minimum detection value that can be obtained.

All analysis was carried out using Statistical Package for the Social Sciences for Windows, version 25.0 (SPSS, Inc., Chicago, IL, USA) to analyze the effectiveness of the coating in reducing the contamination level of the surface. The total bacteria count on the patient partition curtains was compared to the control and treatment group using Mann-Whitney test and T-test. Chi-square test and Fisher's exact test were also used to compare categorical variables such as the percentage of MRSA. Parametric test was carried out to evaluate the cleanliness baseline in each of the wards before and after treatment. ANOVA analysis allowed the comparison of different periods of study and the differences among wards. Median time to first contamination (days) of MDRO for each curtain type was compared using the Wilcoxon rank-sum test. The significance of the statistical test was defined to have a P value <0.05.

Healthcare workers from the participating wards were assessed for their acceptance of the multilevel antimicrobial disinfectant coating by way of a questionnaire. Additional reformulation may be necessary to increase the acceptability of the coating technology to the healthcare workers.

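### The ANOVA compares phases, weeks and wards without naming arm, so it cannot answer the over-time objective or separate loss of coating effect from ordinary build-up

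*Combined protocol and SAP*

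**What the plan says.** The ANOVA is described twice, with different factors. Data Analysis: "ANOVA analysis allowed the comparison of different periods of study and the differences among wards". Detailed Description, paragraph [7]: "ANOVA analysis allowed the comparison of different periods of study of phase wise as well as week wise". Neither place writes out a model, and neither lists arm or an interaction of arm with phase or week.

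Data Analysis introduces the whole set of SPSS analyses as being run "to analyze the effectiveness of the coating in reducing the contamination level of the surface". Arm itself is handled by separate tests: the total count "was compared to the control and treatment group using Mann-Whitney test and T-test". No time term is attached to them.

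On the setting, Detailed Description [2] states: "The study was conducted in the rehabilitation ward of the Kowloon Hospital including both male and female cubicles". Sampling Arrangements and methods, item 1, adds that "one male cubicle (3rd cubicle) and one female cubicle were allocated for this study after pilot study results" and places both in ward 3B. Item 6 gives each cubicle its own samplers: "In the female cubicle, two female team members took samples", with male members sampling the male cubicle.

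The work plan table puts the phases in December 2017, February–March 2018 and May–June 2018, with half the curtains coated in each. Objective 1(i) compares coated with standard curtains on total count followed over time. The second primary outcome, durability, is the change over time within treated curtains during each phase.

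**The concern.** One of the two factors in the Data Analysis version does not exist in this study: there is a single sampled ward. The other, study period, is a calendar factor. With the arms split equally within each phase, a test of phase that leaves arm out compares December with February–March and May–June. It says nothing about whether coated and standard curtains differ, or whether their difference changes.

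The week-wise comparison has the same weakness. Counts on a newly hung curtain can rise from week to week because curtains get dirty, coated or not. A rise among treated curtains alone could be loss of coating effect or that ordinary build-up.

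Two aims are therefore left without a matching analysis. Objective 1(i) is an arm-by-time question, and no listed test of the count contains both arm and time. A durability claim needs the control curtains as reference. A phase or week P-value listed among effectiveness analyses could also be taken for evidence about the coating.

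**Working it through.** **Ward factor.** One ward is sampled, so the degrees of freedom are 1 − 1 = 0. The plural also appears in the baseline-cleanliness sentence and the questionnaire paragraph, but no second sampled ward is described. If cubicles are meant, there is one male and one female cubicle, each with its own team, so cubicle, patient sex and sampler cannot be separated.

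**The plan's own figure.** The sample size section gives 1084 specimens. With d = 0.2, one-sided α = 0.05 and power 0.95, the exact noncentral t gives 542 per group, 1084 in total, critical t 1.64626, δ = 3.29242 and power 0.95007. It reproduces, but it belongs to the two-group t-test. No figure is given for the ANOVA.

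**Phase-only ANOVA.** Inputs: 480, 576 and 768 swabs (work plan; sum 1824), SD 1 log (sample size assumption), two-sided α = 0.05, swabs independent as in the plan's calculation. The shift sizes are assumptions, because the documents give none.

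Noncentrality λ = Σ nᵢ(μᵢ − μ̄)²/SD², referred to a noncentral F with 2 and 1821 df (critical F 3.0007).

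| Scenario (log10) | Pooled phase means | λ | P(significant) |
|---|---|---|---|
| No coating effect, calendar shift 0.1 | 0 / 0.05 / 0.1 | 3.01 | 0.322 |
| No coating effect, calendar shift 0.2 | 0 / 0.1 / 0.2 | 12.03 | 0.883 |
| No coating effect, calendar shift 0.3 | 0 / 0.15 / 0.3 | 27.06 | 0.998 |
| Coating effect 0.4 / 0.2 / 0, no calendar shift | −0.2 / −0.1 / 0 | 12.03 | 0.883 |

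In the last row only half the curtains are coated, so each pooled mean moves by half the effect. Rows 2 and 4 have the same spacing of means and the same λ, so a phase-only test cannot tell them apart.

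**Adding arm.** Simulation with the same sizes, split 1:1, 2000 runs per scenario; rejection rates at 0.05:

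| Scenario | Phase only | Arm adjusted for phase | Arm-by-phase |
|---|---|---|---|
| No effect, no trend | 0.06 | 0.05 | 0.05 |
| Constant 0.2 log effect, no trend | 0.04 | 0.99 | 0.05 |
| No effect, trend 0 / 0.15 / 0.30 | 1.00 | 0.05 | 0.05 |
| Effect 0.4 / 0.2 / 0 masked by trend 0 / −0.1 / −0.2 | 0.04 | 0.95 | 0.88 |

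The phase-only test ignores a constant coating effect, responds to calendar alone, and can miss a fading effect.

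**Weeks.** Let counts build up by g log per week on any curtain and the coating lose h log per week. Coated curtains rise by g + h, standard curtains by g. Treated curtains alone estimate g + h; only (g + h) − g = h, the arm-by-week contrast, isolates the coating.

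**Precision at curtain level.** Each curtain gives 8 areas × 3 weeks = 24 swabs, and there are 20, 24 and 32 curtains per phase. With total SD 1 and intra-curtain correlation ρ (assumed), a curtain mean has variance (1 + 23ρ)/24. For the 0.4 / 0.2 / 0 pattern, λ = Σ wᵢ(eᵢ − ē)², with wᵢ = kᵢ/(4 × variance), kᵢ the curtains in phase i and ē the weighted mean effect; F has 2 and 76 − 6 = 70 df.

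| ρ | Variance | λ | Power of arm-by-phase |
|---|---|---|---|
| 0 | 0.0417 | 12.03 | 87% |
| 0.05 | 0.0896 | 5.59 | 53% |
| 0.1 | 0.1375 | 3.64 | 37% |
| 0.2 | 0.2333 | 2.15 | 23% |

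At ρ = 0.1 the approximate 95% CI half-width for each phase's difference, 1.96 × √(4 × 0.1375/k), is 0.33, 0.30 and 0.26 log.

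**The case against.** Whether the coating works is not left to the ANOVA. It is tested by Mann-Whitney and t-test against concurrent controls, half the curtains in every phase, hung alternately in the same cubicles. Calendar differences do not bias that contrast, and neither does having a separate team for each cubicle. This stands. A reader might infer that the trial cannot show whether the coating works; the documents do not support that.

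No model is written, so the absence of arm is read from the factors named. The ANOVA may have been run within arms or with arm included, and the durability outcome suggests a within-treated use. This stands as a limit on certainty. A within-treated analysis would still not separate g from h.

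No text says that a phase P-value counts as evidence of efficacy; the link is one general sentence covering all analyses. The 32%, 88% and 99.8% figures are power to detect shifts that were assumed, which a comparison of periods is meant to detect. They show what the test responds to, not an error rate of the trial. Both points stand.

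Consistency across phases is not a stated objective, and curtains are changed at the start of each phase, so a fall between phases is not the durability outcome. This too stands, and it makes arm-by-week at least as important as arm-by-phase. It leaves untouched the gap on objective 1(i).

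**Conclusion.** The concern holds for the ANOVA and for the over-time questions. The ward comparison cannot be made (0 degrees of freedom). As described, the phase and week comparisons carry no information on the coating: a 0.2 log calendar shift and a 0.4 / 0.2 / 0 fading effect both give 88%. Objective 1(i) has no matching test, and loss of coating effect over weeks cannot be separated from ordinary build-up.

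This rests on reading the named factors as the whole model. The percentages also rest on assumed shifts, SD 1 log and independent swabs; clustering within curtains would change them but not the logic. The overall arm comparison is unaffected by this point.

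**What to change.** Delete the comparison among wards and replace the ANOVA sentences in both sections with one specification: a mixed model of log10 counts with arm, phase, week, cubicle, arm-by-phase and arm-by-week as fixed effects and a random curtain effect. Cubicle is a blocking factor only, with no P-value for male versus female.

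Report the coated-minus-control log difference with a 95% CI for each phase and each week. Do not read a non-significant interaction as proof of consistency: power for a vanishing effect is only 23% to 53% at assumed intra-curtain correlations of 0.2 to 0.05. Do not cite a phase or week P-value as evidence of effectiveness.

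A model on curtain means with arm-by-phase alone would not be enough, because averaging over the three weekly samples discards the week-wise comparison and the durability outcome.

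Cost: the same data and slightly more analysis work. Interaction estimates will be imprecise with 76 curtains. The study status is completed, so the model should be labelled post hoc.

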## **Study Objectives**

1) To compare the antibacterial effect of in use antimicrobial coated patient privacy curtains with standard curtains:

- i) Total bacterial count over time
- ii) Time of first MDRO contamination
- iii) Percentage of MDRO contamination

2) To assess healthcare worker's acceptance of the multi-level antimicrobial coating.

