## **Inclusion Criteria**

For the clinical setting of the allocated ward with a prior history of high MDRO (preferably MRSA) prevalence is included.

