## 2. Curtain installation:

1. Every 3rd week, our team changed the curtains from 2 cubicles (1 male and one female) according to curtain changing policy of hospital.
2. At the start of every phase of study, following the standard protocol; after taking official consent from ward manager we changed the curtains at once from both cubicles.
3. There were two types of curtains clippings, with metal ring and cloth strips so that curtains were changed according to the type of clips/ring.
4. As there was the capacity of 12 curtains in one cubicle, so six curtains were coated and six uncoated. The sequence was alternative as one coated next uncoated and so on. After installation, we informed ward manager about completion of curtain hanging in the designated ward and took first sample at day 7 because we gave sufficient time to curtains to be contaminate in hospital environment.
5. There was a backup pair of the curtain in case of need to change curtain due to spoilage, vomitus, blood or MDRO diagnosed the patient. Staff was informed to notify our team about the date and reason of curtain changing.

[figure not shown]

Fig 2. Illustration of curtains installation in cubicles as one control other treatment showing matched paired randomization

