**Environmental Sampling:**

1. Sampling Frequency: Curtains were sampled on a weekly basis for the total duration of 3 weeks. So, every curtain was sampled three times during complete sampling duration. First 7 days was the time of exposure to contaminate leading with next 3 weeks of sampling.
2. Sampling Area: Each curtain was sampled for eight areas for the size of 50x50cm^2 each. Four areas from top side starting from patient’s head side to toe side on the bed, and four areas from bottom side moving from toe to head side. As the size of curtain varies from 430cm to 480cm in length, for the best results after pilot study, we calibrated 8 areas keeping 50 cm from above, 37cm from lateral margins and 57-70cm in between.

- Area 1: Upper Head side
- Area 2: Upper 2nd area
- Area 3: Upper 3rd area
- Area 4: Upper Toe Area

- Area 5: Lower Toe Side
- Area 6: Lower 2nd area
- Area 7: Lower 3rd area
- Area 8: Lower Head Area

[figure not shown]

Fig 3. Illustration of 8 sampling location on a curtain received from Rehabilitation ward of KH, Designated 50x50cm^2 area were sampled following the protocol

3. Sampling Side of the curtain: Sampling was done from the inner side of the curtain, (inner side was more exposed to the risk of contamination as a frequent touch of the patient on the bed, nursing staff, cleaning staff, monitoring staff, attendants, and doctor).
4. Sampling material: Polywipe sponge were used to sample 50x50cm^2 area on the curtain.
5. Sampling technique: Both sides of a sponge were used by swabbing on the curtain. Holding the sponge from the middle of one side with the right hand, keeping vertically, swab area starting from upper left margin towards the upper right margin of 50x50cm^2 area from one side of the sponge. The same method was used swabbing from right to left side with other side of the sponge. Sampling was done gently, slowly and softly by not repeating the swab to sampled area.
6. Sampling frame: 50x50cm^2 frame of plastic covered with a disposable plastic sheet was used as back support for smooth sampling and accurate measurement. Every time, sterilized plastic was removed and new sheet was used to reduce the chance of microbial spread or false positive result on control and treatment arm of the study

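### Objective 1(ii) pairs a median in days with a rank-sum test on three possible sampling days, so the reported effect and the P value need not agree

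*Combined protocol and SAP*

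**What the plan says.** Study Objectives 1(ii) is "Time of first MDRO contamination", coated against standard curtains. The only analysis given for it is in Data Analysis: "Median time to first contamination (days) of MDRO for each curtain type was compared using the Wilcoxon rank-sum test". The criterion there is "The significance of the statistical test was defined to have a P value <0.05", with no sidedness stated. No other effect measure or confidence interval is named for this objective, and no rule covers curtains never found positive or replaced early.

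The schedule fixes what can be observed. Under Curtain installation, item 4, the team "took first sample at day 7 because we gave sufficient time to curtains to be contaminate in hospital environment". Environmental Sampling, item 1, says "Curtains were sampled on a weekly basis for the total duration of 3 weeks" and that "every curtain was sampled three times during complete sampling duration". The first positive swab can therefore fall only at about day 7, 14 or 21. Another sentence in the same item could be read as days 14, 21 and 28, but that is still three values.

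The only MDRO plated from the curtains is MRSA, on selective agar. Eight areas are swabbed on each curtain at each visit.

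**The concern.** The median and the rank-sum test summarise different things here. On a three-point scale the median stays put or moves by whole visits (a midpoint such as 10.5 arises only if exactly 19 of 38 curtains fall on one side). The rank-sum test uses the whole ordering of first-positive visits. Its null is equal distributions, and it is a test of medians only under a pure location shift, which a floor at the first swab rules out.

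Two misleading reports could follow. One is 7 versus 7 days with P below 0.05, where the effect measure shows no delay although the arms differ. The other is 7 versus 14 days with a large P value, where a one-week delay rests on two curtains. In neither case does the reported figure tell the reader how large the difference is. Nothing before the first swab is observed, so a value of 7 days means positive by day 7 and is not a contamination time.

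**Working it through.** **Inputs from the documents.** There are 76 curtains (Detailed Description [5]; 20 + 24 + 32 in the work plan), half of them coated, so 38 per arm. There are 8 areas and 3 visits: 76 × 8 × 3 = 1824 samples, as stated. Alpha is 0.05, taken as two-sided because the analysis section does not say.

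**The plan's own figure.** There is no sample size, power or expected rate for this endpoint. The stated 542 per group (1084 in total) is for log total bacteria count. It reproduces with d = 0.20, one-sided alpha 0.05 and power 0.95, and does not bear on this point.

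**Example 1: equal medians, small P.** Counts at day 7/14/21/never, with never-positive curtains ranked last: control 30/4/2/2, coated 20/8/5/5.
- Medians: the 19th and 20th ordered values are day 7 in both arms, a difference of 0 days.
- Pairs in which the control curtain is later: 4×20 + 2×28 + 2×33 = 202. Tied pairs: 600 + 32 + 10 + 10 = 652. U = 202 + 652/2 = 528, against an expected 38×38/2 = 722.
- Tied groups are 50, 12, 7 and 7, so Σ(t³ − t) = 124950 + 1716 + 336 + 336 = 127338. Variance = (1444/12) × [77 − 127338/(76×75)] = 120.33 × 54.66 = 6577, SD 81.1.
- z = (194 − 0.5)/81.1 = 2.39, **p = 0.017**. The probability that a coated curtain is later, counting ties as half, is 1 − 528/1444 = 0.63.

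**Example 2: different medians, large P.** Control 20 at day 7 and 18 at day 14; coated 18 and 20.
- Medians are 7 and 14 days.
- U = 18×18 + (20×18 + 18×20)/2 = 684. Two tied groups of 38 give Σ(t³ − t) = 109668. Variance = 120.33 × (77 − 19.24) = 6950, SD 83.4.
- z = (38 − 0.5)/83.4 = 0.45, **p = 0.65**.

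**How often.** The documents give neither swab positivity q nor within-curtain clustering, so both are assumed and shown as a range. A curtain is positive at a visit with probability 1 − (1 − q)⁸. For q = 30% this is 0.94, and for q = 15% it is 0.73. With independent swabs the true median is the first visit whenever q exceeds 1 − 0.5^(1/8) = 8.3%. Clustering is modelled by a beta-distributed q for each curtain. The table gives the simulated chance of equal medians and rejection in the same trial:

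| q control vs coated | independent | ICC 0.1 | ICC 0.3 |
|---|---|---|---|
| 30% vs 15% | 76% | 68% | 9% |
| 25% vs 12.5% | 75% | 43% | 1% |
| 20% vs 10% | 54% | 10% | 0% |

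With low detection the mismatch returns because neither median is reached by day 21. At per-visit curtain detection of 0.15 vs 0.05 it occurs in 59% of trials, and at 0.10 vs 0.02 in 73%. In between (0.60 vs 0.30, or 0.40 vs 0.20) it occurs in about 1% or less, because the medians usually separate.

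**Test validity.** With the same distribution in both arms the test rejected in 3–5% of simulated trials.

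**The case against.** The strongest reply is that a median beside a rank-sum P value is conventional, that the test is valid for its own null, and that the coincidence needs conditions the documents do not establish. Both medians sit at the first visit only if about half or more of the curtains of each type are MRSA-positive at the first swab. The Inclusion Criteria phrase "prior history of high MDRO (preferably MRSA) prevalence is included" describes the ward's history, not curtain swabs. Only 100 µl of the 10 ml neutralizer reaches each MRSA plate, about 1%, so light contamination can be missed. This stands: the frequency is unknown, and strong clustering makes the day-7 form rare.

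A reader might go further and infer that rejecting in three-quarters of trials with equal medians means a greatly inflated type I error. The documents do not support that. In those scenarios the coating truly halves positivity, so the rejections are power against a real difference.

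A reader might also infer that a real effect would be hidden altogether. That is not supported either. Objective 1(iii) covers the percentage of MDRO contamination, Data Analysis compares MRSA percentages by chi-square and Fisher's exact tests, and MRSA is part of primary outcome 1.

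The reply does not remove the mismatch. Both examples use the trial's own size and schedule, and those percentage comparisons do not address when contamination first occurs.

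**Conclusion.** The point holds as a fault in the effect measure reported for objective 1(ii). At 38 curtains per arm the plan can yield 7 versus 7 days with p = 0.017, or 7 versus 14 days with p = 0.65. Neither median difference conveys what the test assessed.

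The two examples rest on 38 curtains per arm, a two-sided test and, in the first, never-positive curtains ranked last. The frequencies rest on assumed positivity and clustering, and for a halving of positivity from 20–30% they run from 0% to 76%. Reading the visits as days 14, 21 and 28 changes the labels only.

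The consequence is limited. Time to first MDRO contamination appears under Study Objectives but not among the Primary or Secondary Outcome Measures, so the total-count result and the sample size are unaffected. The change is still worth making, because it is cheap and the median cannot reliably show the delay the objective asks about.

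**What to change.** In Data Analysis, replace the comparison of medians for objective 1(ii) with:
- the cumulative percentage of curtains first found MRSA-positive by each of the three visits, by arm;
- one effect estimate with a 95% CI from a discrete-time (complementary log-log) model for visit of first positive, with the curtain as the unit and terms for visit, arm, phase and cubicle;
- a stated rule that never-positive curtains are censored after the last visit and replaced curtains at their last swab. Curtain installation, item 5, allows replacement when a patient is diagnosed with an MDRO, so this censoring may be informative; give the number and reasons by arm.

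If the rank-sum test is kept, state its null as equal distributions over the three visits. Label the first-visit result 'positive by the first swab', and reconcile the two descriptions of the sampling days.

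The cost is a change of wording and one model on data already collected, with no new samples. The downside is that a ratio and three percentages replace a single figure in days. The single ratio also assumes a constant effect across visits, which the visit-wise percentages let the reader judge.
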